2.0	17 Aug 2021	 The following describes the changes that have been made to the SAP between versions 1.0 and 2.0. The following edits were made to correct mistakes in V1.0 of the SAP. Transfer policy deviations will not be considered during the assessment of major or minor deviations. Because transfer occurs after the primary endpoint assessment, a transfer policy deviation cannot impact the primary endpoint. There were cases where "Stimulation Day 5" was used. These cases have been updated to reflect that measurement occurs on "Stimulation Day 6". In V1.0 of the SAP, for the multiple imputation sensitivity analysis, the imputation model (negative binomial) and the analysis model (ANOVA) did not align. In V2.0 of the SAP, the imputation model has been changed to align to the analysis model (both are now an ANOVA model). The following edits were made to clarify the original intent of SAP V1.0. For a subset of inferences, the within-treatment group 95% confidence intervals (adjusted for stratification factors) will be displayed. The subset of inferences is now better defined in V2.0 of the SAP. If the Safety analysis set is identical to the mITT analysis set, tables based on the mITT analysis set will be produced. (The identical tables based on the Safety analysis set will be suppressed.) Trial population, efficacy, and safety summaries will 	1.0
		• That population, efficacy, and safety summaries will be produced that are broken out by age strata.	

	 Presentation of NIMPs taken prior to randomization will include a summary for all subjects exposed, whether or not they were randomized. A listing of protocol deviations due to COVID-19 will be included. In V1.0 of the SAP, the primary endpoint model was described as a 'linear model'. In V2.0 of the SAP, the primary endpoint model has been explicitly defined as an ANOVA model. In V1.0 of the SAP, the analysis method for the secondary pregnancy endpoints and any other dichotomous endpoint was omitted. In V2.0 of the SAP, these secondary efficacy analyses have been defined to use the Mantel-Haenszel method. In several sections, the presentation of subgroup summaries is requested. V2.0 of the SAP clarifies that these subgroups begin with the mITT analysis set prior to subsetting. Inference is performed on complete analysis sets and not on subgroups. The categories for the frequency table summary of the number of 2PN and the number of MII have been aligned with the same for oocytes retrieved. The analysis of inseminated oocytes has been removed as this was never listed as an endpoint. Additional details have been added for the modeling of change from baseline in endocrine laboratory parameters. Ranges for markedly abnormal vital signs and 	
	defined to use the Mantel-Haenszel method.	
	• In several sections, the presentation of subgroup summaries is requested. V2.0 of the SAP clarifies that these subgroups begin with the mITT analysis set prior to subsetting. Inference is performed on complete analysis sets and not on subgroups	
	• The entropy for the frequency table summary of	
	 The categories for the frequency table summary of the number of 2PN and the number of MII have been aligned with the same for oocytes retrieved. The analysis of inseminated oocytes has been removed as this was never listed as an endpoint. Additional details have been added for the modeling of change from baseline in endocrine laboratory parameters. 	
	Ranges for markedly abnormal vital signs and laboratory parameters have been added as an	

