7.2.5 Number and Size of Follicles during Stimulation

Transvaginal ultrasound will be performed at all visits during the stimulation period to count the number of follicles and measure the size of the follicles.

The total number of follicles and number of follicles with a diameter of ≤ 9 mm, 10-11 mm, 12-14 mm, 15-16 mm, and ≥ 17 mm on stimulation day 6 and last day of stimulation will be recorded. Data will be recorded separately for the right and left ovary.

Date: 14 Oct 2019 E-Study Protocol-21539; Ver. 6.0 Supersedes: 5.0 Page 59 of 103

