7.2.6 Oocytes Retrieved

The number of oocytes retrieved will be recorded at the oocyte retrieval visit.

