9.1 Determination of Sample Size

The present trial is a pharmacodynamic comparison of a marketed product to a new formulation of the same. With 188 subjects per treatment group, the trial has at least 85% power to demonstrate the non-inferiority of MENOPUR liquid to MENOPUR powder in the number of fertilized oocytes at the 1-sided significance level of 0.025. This is based on the results for MENOPUR powder from the COMBINE trial conducted in a similar setting (GnRH agonist protocol, MENOPUR starting dose of 225 IU for the first five days, insemination by ICSI etc.) and in a similar population (infertile women between 18 and 42 years). The mean (SD) of the number of fertilized oocytes were 7.88 (5.15) with similar results in the two age groups (7.92 in the <35 years age group vs. 7.80 in the ≥35 years age group). The non-inferiority margin of -1.60 will retain 80% of the expected comparator effect.

After adjusting for 5% missing data, approximately 400 subjects will be randomized (1:1) into this trial, stratified by trial site and age (<35years and ≥35 years).

A blinded sample size reassessment will be done when data on the primary endpoint are available for 70% of the planned subjects or when 300 subjects are randomized, whichever comes first. The sample size reassessment will be done without breaking the blind and without inflating the type I error of the trial, in line with current regulatory guidelines. The expected maximum number of subjects to be randomized is 500 (250 subjects per treatment group), corresponding to a blinded one-sample (both groups pooled) standard deviation estimate of 5.8 and 85% power.

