9.2.2 Sensitivity Analyses

Four sensitivity analyses will be conducted. The first two sensitivity analyses will repeat the primary analysis but will use the ITT and PP analysis sets.

The third sensitivity analysis will repeat the primary analysis using the mITT analysis set, but will apply a different method of imputation for missing data. The primary analysis treats all missing primary endpoints as having observed zero 2PN. There are instances, however, where the number

of 2PN for a subject with a missing primary endpoint could theoretically have been greater than zero. Such instances may include: withdrawal of consent, being lost to follow-up, having the study terminated by the sponsor, not attending key visits, due to the COVID-19 pandemic trial hold, or other reasons that would cause a subject with a potential non-zero 2PN count to have a missing value. The temporal nature of the above stated reasons for missing a non-zero 2PN count are such that a subject would need to have taken one or more doses of IMP and have a missing primary endpoint. A sensitivity analysis for the primary endpoint will be performed by using the multiple imputation approach which could impute a non-zero value for missing primary endpoints where it can be reasonably expected that the true value would have been non-zero. The following steps will be taken to implement the multiple imputation method:

- Imputation phase An ANOVA model with factors for treatment group, age strata, and center will be fitted to data from subjects in the mITT analysis set, less those subjects with missing primary endpoints. For each missing primary endpoint, a total of 1000 draws will be made from a normal distribution that is characterized by the estimated parameters from the fitted model and the factor values associated with the missing record. A total of 1000 complete datasets will be constructed.
- Analysis phase Each of the 1000 complete datasets will be analyzed using the ANOVA model described in Section 9.1.2.
- Pooling phase The estimated mean differences and standard errors from the analysis phase will be combined using Rubin's formula (Rubin 1987):

$$m_{MI} = \frac{1}{1000} \sum_{i=1}^{1000} m_i$$

$$se_{MI} = \sqrt{\frac{1}{1000} \sum_{i=1}^{1000} se_i^2 + \left(1 + \frac{1}{1000}\right) \left(\frac{1}{1000 - 1}\right) \sum_{i=1}^{1000} (m_i - m_{MI})^2}$$

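### The multiple-imputation sensitivity analysis in SAP 9.2.2 uses no recorded ovarian-response data, so its point estimate is simply the complete-case estimate

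*SAP*

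**What the plan says.** SAP 9.2.1 scores every missing 2PN count as zero and analyzes the mITT set with an ANOVA on treatment, age strata and center. SAP 9.2.2 adds four sensitivity analyses. The ITT, per-protocol and 95.08% interval analyses all repeat the primary analysis and leave the zero rule in place. Only the third replaces it, with multiple imputation.

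Its aim is an approach "which could impute a non-zero value for missing primary endpoints where it can be reasonably expected that the true value would have been non-zero". For the imputation phase, "An ANOVA model with factors for treatment group, age strata, and center will be fitted" to the mITT women whose count is observed. Each missing count is drawn 1000 times from a normal distribution at the fitted estimates. Each completed dataset then goes through the ANOVA of SAP 9.1.2, which has the same three factors. The version history (entry for version 2.0) describes the change from a negative binomial imputation model in these words: "the imputation model has been changed to align to the analysis model (both are now an ANOVA model".

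The trial records how each woman responded before fertilization is read. Protocol 7.2.5 has follicle counts by size that "on stimulation day 6 and last day of stimulation will be recorded". Protocol 7.2.6 states: "The number of oocytes retrieved will be recorded at the oocyte retrieval visit". Protocol 7.2.7 records oocyte maturity before ICSI, and Protocol 7.3.10 has AMH at screening and on day 1. None of these enters the imputation.

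**The concern.** Imputation tells us more than dropping the incomplete women only if the imputation model knows something that the analysis model does not. Here both contain the same factors. Two women in the same arm, age stratum and center get the same imputation distribution, even if one had few growing follicles on day 6 and the other had many. Age stratum, the only patient characteristic in the model besides arm, hardly separates the planning means (7.92 against 7.80 in Protocol 9.1). The model therefore has almost nothing with which to judge whose count was likely to be above zero.

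At stake is the value of the one planned check on the zero rule. Because it assumes that women with missing counts responded like the rest of their arm, it is off target if response-related loss differs between arms. SAP 9.2.2 itself tabulates 2PN counts by oocytes retrieved and by day-1 AMH, so the plan already treats these variables as relevant to the endpoint.

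**Working it through.** **1. The plan's own figure.** Protocol 9.1 gives "With 188 subjects per treatment group, the trial has at least 85% power", "at the 1-sided significance level of 0.025", with margin 1.60. It adds: "The mean (SD) of the number of fertilized oocytes were 7.88 (5.15"; the second number is the SD. SAP Appendix 1 assumes a true difference of 0.

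n per arm = 2 × (1.960 + 1.036)² × 5.15² / 1.60² = 2 × 8.978 × 26.52 / 2.56 = 186.0, so 187 by the normal approximation. With the noncentral t, 187 gives 84.999% and 188 gives 85.2%. The stated 188 is reproduced. 188 / 0.95 = 197.9, so 198 per arm, about 400 in all.

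**2. Why the estimate equals complete case.** Let b be the least-squares fit to the women with observed counts, so that X_obs′(y_obs − X_obs b) = 0. Fill each missing count with its fitted value X_mis b. The added residuals are zero, the normal equations still hold at b, and the refit returns b exactly. Random draws add only (X′X)⁻¹X_mis′e, which has mean zero and is averaged over 1000 datasets.

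Numerical checks (400 women, 25 centers, mean 7.88, SD 5.15):
- Filling with fitted values: largest deviation from complete case 8 × 10⁻¹⁴.
- 1000 draws, 5% missing: mean absolute deviation 0.003, maximum 0.017 oocytes.
- 1000 draws, 10% missing: mean 0.004, maximum 0.019.
- Standard errors at 5% missing: about 0.546 (imputation) and 0.548 (complete case).

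**3. Is the change to ANOVA the cause?** A negative binomial imputation with the same three factors (an assumption, since the version 1.0 covariates are not stated) stayed within 0.014 of complete case in 60 simulated trials. The family hardly matters. The covariates do.

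**4. Size under assumed missingness.** The documents give no arm-specific or response-specific missingness, so the following are assumptions. Let z be a standardized response with correlation ρ to the 2PN count, and let the chance of a missing count be proportional to exp(−z). Then z has mean −1 among the missing women, whose mean count is lower by 5.15ρ. With missing fraction f, the complete-case mean of an arm is too high by 5.15ρ × f/(1 − f).

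For 8% missing on liquid and 2% on powder:
- Planned imputation: 5.15ρ × (0.08/0.92 − 0.02/0.98) = 5.15ρ × 0.0666 = 0.343ρ.
- With a proxy correlating 0.6 with z in the imputation model: a fraction 0.6² = 0.36 is removed and 0.64 remains.
- Zero rule (primary analysis): −(0.08 − 0.02) × (7.88 − 5.15ρ).

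| ρ | Planned: formula (simulated) | With 0.6 proxy: formula (simulated) | Zero rule: formula |
|---|---|---|---|
| 0.5 | +0.17 (0.17) | +0.11 (0.11) | −0.32 |
| 0.7 | +0.24 (0.23) | +0.15 (0.15) | −0.26 |
| 0.85 | +0.29 (0.28) | +0.19 (0.18) | −0.21 |

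Positive values favor liquid. Simulation of the zero rule gave about −0.21 to −0.32. As a share of the margin, the planned imputation errs by 0.17/1.60 = 11% to 0.28/1.60 = 18%. With 5% against 1% missing, the simulated errors are 0.11 to 0.19. With z itself in the imputation model they are within 0.005 of zero. With equal missingness in both arms, the error is about zero with or without z.

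A harsher assumption (5% missing, low responders lost on liquid and high responders on powder) gives 0.20, 0.38 and 0.53 at correlations 0.3, 0.6 and 0.8. The documents give no reason to expect that pattern.

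**The case against.** The case for leaving the text alone is substantial, and most of it stands.

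- **A contrast with the zero rule is what is wanted.** Assuming that missing women resemble others in their arm, stratum and center provides one. Leaving out auxiliary variables is not an error or a contradiction.
- **The listed reasons are mostly administrative**: withdrawn consent, loss to follow-up, sponsor termination, missed visits, the pandemic hold. The trial is double-blind and double-dummy, compares two formulations of one drug substance, and plans for 5% missing. A fourfold difference between arms is an assumption.
- **The strongest predictors will seldom be available.** ICSI follows retrieval by 4±2 hours, and fertilization is read in the laboratory 19±2 hours later without a further visit. A woman with a missing count will rarely have oocytes retrieved on record. The remedy rests mainly on AMH and follicle counts, and day-6 counts do not exist for women lost earlier.

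A reader might infer from the version history that version 2.0 stripped response data out of the imputation. The history records only a change of family, and step 3 shows that the family is not the cause.

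A reader might also infer that the trial is tilted toward non-inferiority. The documents do not support this. Under the mechanism in step 4 the zero-scored primary analysis errs against liquid. With the arms reversed both signs flip, so the two analyses err in opposite directions either way. No decision rule depends on the sensitivity analysis.

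What survives is narrower: the only analysis that relaxes the zero rule cannot do what its own text says it is for, although relevant data are on file.

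**Conclusion.** The point holds as a specification weakness in one sensitivity analysis. Its point estimate is the complete-case estimate for mITT women with an observed count; that is algebra and needs no assumption. It remains informative against the zero rule, so it would be wrong to call it empty, but 1000 imputations tell the reader nothing about the treatment difference that dropping the incomplete women would not.

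The practical size is conditional. About 0.17 to 0.28 oocytes toward liquid requires response-related missingness of 8% against 2% and correlations of 0.5 to 0.85, none of which is in the documents. Nor should a reader expect auxiliary variables to remove the error outright: that happens only if they capture what drives missingness, and a proxy correlating 0.6 with the driver removes roughly a third. The non-inferiority conclusion does not change. This is a worthwhile, inexpensive improvement.

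**What to change.** In the imputation phase of SAP 9.2.2, keep treatment, age strata and center, and add variables already collected, as far as each woman progressed:
- AMH at screening or day 1;
- follicle counts on day 6 and on the last day of stimulation;
- oocytes retrieved and metaphase II oocytes, where they exist.

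Impute sequentially in that order. Keep the analysis ANOVA, the pooling and the primary analysis unchanged. Alignment is preserved, since it requires only that the imputation model contain the analysis factors.

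The same paragraph should say which zero-scored women count as missing, for example whether cancelled cycles do, because the present text does not settle it.

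The cost is SAP wording and modest programming before the blind is broken, with no new data. The downside is a longer imputation model that differs by how far a woman progressed.

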1.1 Definitions/ Abbreviations

1.1.1 Definition of Terms

Terms	Definitions
Baseline	The last available assessed value prior to the first exposure to IMP.

1.1.2 Abbreviations

Abbreviations Meaning of abbreviations in document	
AE	Adverse Event
АМН	Anti-Müllerian Hormone
ART	Assisted Reproductive Technology
ATC	Anatomic Therapeutic Chemical
βhCG	Beta-Human Chorionic Gonadotropin
BMI	Body Mass Index
CRF	Case Report Form
E2	Estradiol
eCRF	Electronic Case Report Form
FDA	Food and Drug Administration
FSH	Follicle Stimulating Hormone
GnRH Gonadotropin-releasing Hormone	
hCG	Human Chorionic Gonadotropin
ICSI	Intracytoplasmic Sperm Injection
IMP	Investigational Medicinal Product
ITT	Intention-To-Treat
IU International Unit	
IUI	Intrauterine Insemination
LH	Luteinizing Hormone
LLOQ	Lower Limit of Quantification
MedDRA Medical Dictionary for Regulatory Activities	
mITT Modified Intention-To-Treat	
NIMP	Non-Investigational Medicinal Product
ΟΙ	Ovulation Induction
P4	Progesterone
PP	Per-Protocol

Ferring Pharmaceuticals

РТ	Preferred Term
SAE	Serious Adverse Event
SD	Standard Deviation
SOC	System Organ Class
ULOQ	Upper Limit of Quantification
WHO	World Health Organization

1.2 Presentation of results

1.2.1 Presentation of descriptive results

Categorical data will be summarized, unless otherwise stated, using the frequency (n) and relative frequencies as a percentage (i.e.; 100*n/N).

Continuous data will be presented for observed values, unless otherwise stated, using the number of subjects (N), number of observations (n), mean and standard deviation (SD), median and interquartile range (IQR), and range (minimum to maximum).

1.2.2 Presentation of inferential results

Inferential results will include confidence intervals for the treatment difference. For a subset of analyses, a within-treatment group confidence interval will be presented.

1.2.3 Subject data listings by domain

Individual subject data will be presented in listings in accordance to ICH E3. Included will be listings of:

- Discontinued subjects
- Protocol deviations
- Subjects excluded from the efficacy analysis
- Demographic data
- Non-investigational medicinal product (NIMP) and investigational medicinal product (IMP) use (with indication of compliance and concentration)
- Individual efficacy response data
- Adverse events by subject (with indication of deaths and serious adverse events [SAEs])
- Individual laboratory measurements by subject (with indication of abnormal values)

2 Trial Objectives and Endpoints

2.1 **Objectives**

Primary Objective

• To demonstrate non-inferiority of MENOPUR liquid versus MENOPUR powder with respect to the number of fertilized oocytes in women undergoing controlled ovarian stimulation.

Secondary Objectives

- To evaluate the pregnancy rates after stimulation with MENOPUR liquid and MENOPUR powder.
- To evaluate the follicular development during stimulation with MENOPUR liquid and MENOPUR powder.
- To evaluate the serum endocrine profile during stimulation with MENOPUR liquid and MENOPUR powder.
- To evaluate the number of oocytes retrieved, the number and quality of embryos, and the number and quality of blastocysts, associated with MENOPUR liquid and MENOPUR powder.
- To evaluate treatment efficiency of MENOPUR liquid and MENOPUR powder.
- To evaluate the safety profile of MENOPUR liquid and MENOPUR powder, including adverse events, routine safety laboratory parameters, local tolerability and immunogenicity.

2.2 Endpoints

Primary Endpoint

• Number of fertilized (2 pronuclei [2PN]) oocytes at 19±2 hours after insemination.

Secondary Endpoints

- Positive βhCG rate (positive βhCG test 10-14 days after blastocyst transfer).
- Clinical pregnancy rate (transvaginal ultrasound showing at least 1 intrauterine gestational sac with fetal heart beat 5-6 weeks after blastocyst transfer).
- Ongoing pregnancy rate (at least one intrauterine viable fetus 8-9 weeks after blastocyst transfer).

Ferring Pharmaceuticals

- Early pregnancy loss (defined as a positive βhCG test but no ongoing pregnancy at 8-9 weeks after blastocyst transfer).
- Follicular development as assessed by transvaginal ultrasound on stimulation day 6 and last day of stimulation.
- Endocrine profile:
 - Serum follicle-stimulating hormone (FSH) on day 6, last day of stimulation and at oocyte retrieval, and corresponding population pharmacokinetics (PK) analysis.
 - Serum Anti-Müllerian hormone (AMH) on last day of stimulation and at end-of-trial.
 - Human chorionic gonadotropin (hCG) and luteinizing hormone (LH) on day 6 and last day of stimulation.
 - Estradiol (E2) and progesterone (P4) on day 6 and last day of stimulation.
- Number of oocytes retrieved, number of metaphase II oocytes, fertilization rate, and number and quality of blastocysts 5 days after oocyte retrieval.
- Total gonadotropin dose and number of stimulation days.
- Frequency of OHSS (early OHSS if the onset is ≤9 days after triggering of final follicular maturation and late OHSS if the onset is >9 days after triggering of final follicular maturation).
- Frequency and intensity of adverse events.
- Changes in circulating levels of clinical chemistry and hematology parameters and proportion of subjects with markedly abnormal changes.
- Frequency and intensity of injection site reactions (redness, pain, itching, swelling and bruising) assessed by the subject during the stimulation period.
- Frequency of treatment-induced anti-MENOPUR antibodies, overall as well as with neutralizing capacity.
- Technical malfunctions of the pen.

Post-trial Endpoints

- Live birth rate.
- Late pregnancy loss rate (defined as an ongoing pregnancy but no live birth).

• Neonatal health including SAEs at birth, and SAEs at 4 weeks and minimum 6 months after birth.

3 Trial design

3.1 General Design Considerations

Overview of Design Elements

This is a phase 3, randomized, double-blind double-dummy, parallel-group, multicenter noninferiority trial. Approximately 400 females aged 18-42 years undergoing controlled ovarian stimulation as a part of a gonadotropin-releasing hormone (GnRH) agonist protocol at infertility centers in the US will be randomized 1:1 to receive either MENOPUR liquid (including Placebo to MENOPUR powder) or MENOPUR powder (including Placebo to MENOPUR liquid). Randomization will be stratified by trial site and age strata (<35 years and \geq 35 years).

The primary endpoint is the number of fertilized oocytes. Positive β hCG, clinical pregnancy and ongoing pregnancy are included as secondary endpoints in the trial. The secondary endpoints also cover commonly investigated pharmacodynamic parameters such as endocrine profile and ovarian response as well as standard evaluations of safety profile. Furthermore, oocyte and embryo quality will be assessed and a detailed evaluation of blastocyst quality is also included in the trial.

A blinded sample size reassessment will be done when data on the primary endpoint are available for 70% of the planned subjects or when 300 subjects are randomized, whichever comes first. The number of randomized subjects may be adjusted up to a maximum of 500 subjects, corresponding to a blinded one-sample standard deviation estimate of 5.8 and 85% power. No interim analyses intended to compare treatment groups with respect to efficacy or safety are planned.

Subjects are followed through the assessment of ongoing pregnancy. Post-trial follow-up extends to collection of delivery information (live birth and neonatal health), which will be collected for all subjects with an ongoing pregnancy. In addition, data on neonatal SAEs will be collected at 4 weeks and minimum 6 months after birth. Subjects with a treatment-induced anti-MENOPUR antibody response will be followed until the response has become negative or returned to the pre-dosing level, or for a maximum of 1 year.

Additional Design Considerations

Within 3 days of downregulation confirmation (serum E2 \leq 20 pg/mL [central laboratory] and transvaginal ultrasound showing no ovarian cysts), subjects will be randomized to receive either MENOPUR liquid (including Placebo to MENOPUR powder) or MENOPUR powder (including Placebo to MENOPUR liquid) initiated at 225 international units (IU) for 5 days. From stimulation day 6 onward, based on follicular response assessed by transvaginal ultrasound, dosing can be adjusted every second day as needed by 75 IU per adjustment. However, the maximum gonadotropin dose will be 450 IU/day and the minimum dose will be 75 IU/day; gonadotropin dosing can continue for a maximum of 20 days, and coasting is not allowed.

Oocyte retrieval will take place 36 ± 2 hours after triggering of final follicular maturation, and oocytes will be inseminated by intracytoplasmic sperm injection (ICSI) 4 ± 2 hours after retrieval;

oocyte maturity will be recorded. Fertilization (number of pronuclei) will be assessed 19±2 hours following ICSI. Blastocyst quality will be assessed on day 5 following oocyte retrieval.

All subjects will have single blastocyst transfer if they have at least one good-quality (i.e. grade 3BB or above) blastocyst available on day 5 following oocyte retrieval. If no good-quality blastocyst is available, they may have double blastocyst transfer, if at least two blastocysts are available. Transfer of day 6 (or later) blastocyst(s) is not allowed.

Blood samples will be collected throughout the trial for the purpose of evaluating the endocrine profile, clinical chemistry and hematology parameters as well as anti-MENOPUR antibodies. Endocrine parameters (FSH, LH, hCG, E2 and P4) are assessed at baseline (E2 at confirmation of downregulation and FSH, LH, hCG and P4 on stimulation day 1), day 6, and at end-of-stimulation (day of trigger), and furthermore, FSH is also assessed at oocyte retrieval. In addition, AMH is assessed on stimulation day 1, on the last day of stimulation, and at end-of-trial. Clinical chemistry and hematology are assessed at screening, last day of stimulation, and end-of-trial. Anti-MENOPUR antibodies are assessed at four occasions. The first sample is taken at the screening visit and is exclusively used to re-establish the anti-drug antibody analytical assays. The subsequent three samples are used for analysis of anti-MENOPUR antibodies in the individual subjects in the trial, and are taken prior to dosing on stimulation day 1 and at two occasions post-dosing: 7-10 days after the last MENOPUR liquid or MENOPUR powder dose (this may coincide with the transfer visit) and 21-28 days after the last MENOPUR liquid or MENOPUR powder dose (this may coincide with the ßhCG test visit). Subjects with a treatment-induced anti-MENOPUR antibody response will be followed until the response has become negative or returned to the pre-dosing level.

Local tolerability of MENOPUR liquid or MENOPUR powder following subcutaneous administration will be assessed by the subject three times daily: immediately, 30 minutes and 24 hours after each injection. The assessment of injection site reactions will be made throughout the stimulation period and recorded by the subject in a diary.

Concerning post-trial follow-up, all subjects with an ongoing pregnancy will be followed. Data will be gathered on delivery information (live birth and neonatal health). In addition, data on neonatal SAEs will be collected at 4 weeks and minimum 6 months after birth.

